1.1. Sponsor Name

Hangzhou Endonom Medtech Co., Ltd.

4.1. Objectives

The purpose of this clinical trial is to evaluate the safety and efficacy of the WeFlow-Tribranch embedded aortic Triple-branch arch Stent Graft system developed and manufactured by Hangzhou Endonom Medtech Co.; Ltd. in the treatment of patients with aortic arch aneurysms.

4.2. Content

This study will be conducted at qualified clinical research institutions. Investigators will perform endovascular treatment in patients with aortic arch lesions using the WeFlow-Tribranch embedded aortic Triple-branch arch Stent Graft system, developed and manufactured by Hangzhou Endonom Medtech Co.; Ltd. This is a prospective, multicenter, single-arm objective performance criterion clinical study. An internet-based registration system

will be used to enroll and document all study subjects. The study is planned to initiate in October 2023, with completion of 90 clinical implantations by December 2025. Clinical follow-up assessments will be performed before discharge, at 30 days, 6 months, 12 months, 24 months, 36 months, 48 months, and 60 months postoperatively. Computed Tomography Angiography (CTA) imaging follow-up will be conducted at 30 days, 6 months, 12 months, 24 months, 36 months, 48 months, and 60 months after the procedure.

The primary endpoint of this trial is the incidence of all-cause death or major stroke within 12 months after surgery. Effectiveness endpoints include the incidence of Type I or Type III endoleak, the incidence of aortic stent graft migration, postoperative branch vessel patency rate, and the rate of conversion to open thoracic surgery or secondary interventional procedures. Safety endpoints comprise all-cause mortality rate, aortic aneurysm-related mortality rate, the incidence of Serious Adverse Events (SAEs), and the incidence of device-related adverse events. After completion of the 12-month primary endpoint evaluation, the sponsor will finalize the clinical study report and submit it to the National Medical Products Administration (NMPA). Annual long-term follow-up will continue up to the fifth year to evaluate long-term clinical outcomes.

5. Background Information Pertaining to the Clinical Trial

Aortic aneurysm (AA) refers to the aneurysmal dilatation of the aorta, generally defined as a dilated diameter exceeding 1.5 times that of the normal vascular lumen. Thoracic aortic aneurysm (TAA) involves the ascending aorta, aortic arch, or descending thoracic aorta. The overall incidence of TAA is approximately 10.4 per 100,000 person-years, among which aortic arch aneurysms account for only about 10% of all TAA cases¹. More than 70% of patients with untreated thoracic aortic aneurysms will eventually progress to aneurysm rupture, and over 90% of ruptures are fatal. The natural growth rate of thoracic aortic aneurysms averages 0.1 cm per year. Consensus recommendations indicate that symptomatic aneurysms or penetrating aortic ulcers (PAUs) should be treated regardless of lesion size².

Based on domestic and international clinical experience, for aortic aneurysms involving the ascending aorta or aortic arch, open surgical repair is conventionally required due to the lack of

adequate proximal landing zones. Open surgical reconstruction for ascending and aortic arch aneurysms relies on deep hypothermic circulatory arrest, with perioperative mortality ranging from 2% to 16.5% and stroke rates from 2% to 18%³⁻⁴. Hybrid arch procedures provide sufficient proximal landing zones for endovascular repair and eliminate the need for deep hypothermic circulatory arrest; however, perioperative mortality (0%–15%) and stroke rates (0%–11%) remain relatively high⁵. In particular, patients with high surgical risks or clear surgical contraindications related to advanced age or comorbidities can only receive conservative medical therapy. A meta-analysis published by Wee I in European Journal of Vascular and Endovascular Surgery in 2019⁶ included 17 studies with a total of 6,894 patients receiving medical management due to advanced age, underlying diseases, controversial diagnoses, refusal of surgery, or insufficient institutional resources. The results demonstrated an in-hospital all-cause mortality rate as high as 39.1%.

In recent years, the development of fenestrated and branched stent grafts has provided novel devices and approaches for aortic arch pathologies⁷⁻⁹, substantially reducing the high mortality associated with open surgery (14% vs. 8%)^{7,10-13}. Endovascular intervention features minimal trauma, fewer complications, lower mortality, and faster postoperative recovery, enabling active treatment for elderly patients or those with cardiac, pulmonary, hepatic, or renal insufficiency. Currently, endovascular repair has become the first-line treatment for anatomically suitable patients with arch disease who are ineligible for open surgery. In routine clinical practice, due to the lack of mature, widely applicable multi-branched endovascular grafts for aortic arch reconstruction, off-label techniques such as parallel stent grafting and fenestration are commonly adopted to treat aortic arch lesions with standard aortic stent grafts. The parallel stent technique preserves branch perfusion and extends the landing zone by deploying small parallel stents (chimney stents) at the junction of arch branch vessels and the main aortic stent graft; nevertheless, gaps between the main graft and chimney stents carry a long-term risk of endoleak. Fenestration can be performed via in-vitro or in-situ approaches. In-vitro fenestration suffers from inaccurate alignment, while in-situ fenestration avoids positioning errors but still has limitations, including the risk of embolic debris from

fenestration and inapplicability to severely tortuous anatomies. With continuous technological innovation, branched stent graft technology—especially multi-branched endovascular aortic arch reconstruction—has emerged as the future direction, owing to its conformity to physiological anatomy and hemodynamics^{14–18}.

Globally, research on multi-branched stent grafts remains in the early stage. For instance, the NEXUS aortic stent graft system by Endospa adopts a modular design for thoracic aortic lesions involving the aortic arch; however, it only reconstructs the brachiocephalic trunk, while the left common carotid artery and left subclavian artery require two additional bypass procedures to maintain cerebral perfusion. Further studies are needed to verify whether the single arterial diameter can fully satisfy perfusion demands of all arch vessels¹⁹. This device has obtained CE (Conformité Européenne) certification and is currently undergoing pivotal clinical investigations under the FDA (Food and Drug Administration) regulatory framework. The Multi-branch dual in-branched stent graft by COOK¹³, the A-Branch triple in-branched stent graft system²⁰, and the RelayBranch stent graft by Terumo are also under feasibility evaluations^{7, 10, 21–23}. Notably, RelayBranch received FDA Breakthrough Device Designation in March 2022; nevertheless, stroke risk remains a critical concern for such products.

Addressing the current limitations of clinical endovascular arch repair techniques and devices, the Modular Integrated Triple-Branched Aortic Arch Stent Graft System investigated in this study integrates in-branch and modular design concepts. The system consists of an integrated ascending aortic stent graft subsystem, an integrated arch stent graft subsystem, branched stent graft subsystems, and aortic extension stent graft subsystems. The integrated ascending aortic stent graft features two built-in branches for endovascular reconstruction of the innominate artery and left common carotid artery via matched branched subsystems, while the integrated arch stent graft reconstructs the left subclavian artery and connects with the ascending module to treat combined arch and descending aortic lesions, achieving total endovascular repair without debranching surgery. The modular integrated vascular design maintains uninterrupted cerebral perfusion during implantation, eliminates the need for deep hypothermic circulatory arrest and thoracotomy, reduces stroke risk, and provides an

innovative therapeutic alternative for patients.

The investigational device has completed registration testing with qualified results for all chemical and physical performance indicators. Preclinical animal studies and benchtop simulation tests have also been finalized, confirming that delivery system navigation, stent positioning, and deployment fully meet clinical operational requirements. Animal studies have verified favorable safety and feasibility. Additionally, comprehensive performance testing conducted by Hangzhou Endonom Medtech Co., Ltd. has confirmed stable product performance and compliant quality. Accordingly, the investigational device satisfies all prerequisites for initiating clinical trials. This clinical trial application is submitted to validate the safety and efficacy of the WeFlow-Tribranch embedded aortic Triple-branch arch Stent Graft system.

6. Product Structural Composition, Working Principles, Mechanism of Action and Scope of Testing

6.1. Product Structural Composition, Working Principles and Mechanism of Action

The WeFlow-Tribranch embedded aortic Triple-branch arch Stent Graft system consists of an integrated ascending aortic stent graft subsystem, an integrated arch segment stent graft subsystem, an aortic extension stent graft subsystem, and a branched stent graft subsystem. The integrated ascending aortic stent graft subsystem is composed of an integrated ascending aortic stent graft and a delivery system, as shown in Figures 1 and 2. The integrated arch segment stent graft subsystem comprises an integrated arch segment stent graft and a delivery system, as shown in Figures 3 and 4. The aortic extension stent graft subsystem includes an aortic extension stent graft and a delivery system, as shown in Figures 5, 6 and 7. The branched stent graft subsystem consists of a branched stent graft and a delivery system, as shown in Figures 8 and 9. The integrated ascending aortic stent graft is equipped with two inner branches, which can reconstruct the innominate artery and the left common carotid artery via endovascular placement of the corresponding branched stent grafts. The integrated arch segment stent graft features one inner branch, enabling endovascular reconstruction of the left subclavian artery with the matching branched stent graft. Combined deployment of the integrated ascending

aortic stent graft, the integrated arch segment stent graft, and the aortic extension stent graft enables the treatment of lesions involving the aortic arch, as illustrated in Figure 10.

[figure not shown]

Figure 1 Embedded Ascending Aortic Stent Graft

[figure not shown]

Figure 2 Delivery System for Embedded Ascending Aortic Stent Graft

[figure not shown]

Figure 3 Embedded Aortic Arch Stent Graft

[figure not shown]

Figure 4 Delivery System for Embedded Aortic Arch Stent Graft

[figure not shown]

Figure 5 Aortic Extension Stent Graft

[figure not shown]

Figure 6 Aortic Extension Stent Graft Delivery System - S

[figure not shown]

Figure 7 Aortic Extension Stent Graft Delivery System - L

[figure not shown]

Figure 8: Branch Stent Graft

[figure not shown]

Figure 9 Delivery System for Branch Stent Graft

Branched Stent Graft

Figure 10 Modular Embedded Triple-Branch Aortic Arch Stent Graft System

6.2. Product Specifications

The product specification series of the Modular Embedded triple-branch aortic arch stent graft system are shown in Tables 1–6.:

Table 1: Specification Series of Modular Embedded Ascending Aortic Stent Graft

Unit: mm

Specifi cation	D1	D2	D	D4	L	Delivery System Specification
28	28					22F
30	30					22F
32	32					22F
34	34					22F
36	36					22F
38	38					24F
40	40					24F
42	42					24F
44	44					24F
46	46					24F

Specifi cation	D1	D2	D	D4	L	Delivery System Specification
48	48					24F
50	50					24F
52	52					24F

Table 2: Specification Series of the Modular Embedded Aortic Arch Stent Graft (I) Unit: mm

Specif ication n	D1	D2	D3	L1	Delivery System Specification
26	26				22F
28	28				22F
30	30				22F
32	32				22F
34	34				22F
36	36				22F
38	38				22F
40	40				24F
42	42				24F
44	44				24F
46	46				24F
48	48				24F
50	50				24F

Table 3: Fenestration Distance List of Modular Embedded Aortic Arch Stent Graft (II) Unit: mm

L1	L2

Table 4: Specification Sheet of Aortic Extension Stent Graft Unit: mm

Specifica tion	D1	D2	L1	Delivery System Specification
26	26			20F
28	28			20F

Specifica tion	D1	D2	L1	Delivery System Specification
30	30			20F
32	32			20F
34	34			22F
36	36			22F
38	38			22F
40	40			22F
42	42			22F
44	44			22F
46	46			22F
48	48			22F
50	50			22F

Table 5: Specification Series of Branch Stent Graft

Unit: mm

Specific ation	D1	D2	L1	Delivery System Specification
7	7			10F
8	8			10F
9	9			10F
10	10			10F
11	11			10F
12	12			10F
13	13			10F
14	14			12F
16	16			12F
18	18			12F
20	20			12F
22	22			14F
24	24			14F
26	26			14F

Table 6: Delivery System Specifications

Unit: mm

Specific ation	Type	OD	L0
22F	Modular Embedded Ascending		
24F	Aortic Stent Graft System		
22F	Modular Embedded Aortic Arch		

Specific ation	Type	OD	L0
24F	Stent System		
20F	Aortic Extension Stent Graft		
22F	System		
10F			
12F	Branch Stent Graft System		
14F			

6.3. Trial Scope

This trial will be conducted at multiple domestic clinical centers, enrolling subjects from vascular surgery wards, cardiac surgery wards, emergency departments and other relevant settings. All subjects shall have a definitive preoperative diagnosis of aortic arch lesions, including true aortic arch aneurysm, pseudo-aortic arch aneurysm, and penetrating aortic ulcer.

7. Product Indications, Contraindications and Precautions

7.1. Indications

Applicable to lesions of the aortic arch, including true aortic arch aneurysm, pseudo-aortic arch aneurysm, and aortic arch ulcer.

7.2. Contraindications

- (1) Patients with acute systemic infection.
- (2) Patients with contraindications to antiplatelet and anticoagulant medications.
- (3) Patients with allergies to contrast agents, anesthetic drugs, or materials of the stent and delivery system.
- (4) Patients with vascular morphology unsuitable for endovascular repair.

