8.1.4. Subject Selection

8.1.4.1. Selection Criteria (All of the following conditions must be met prior to enrollment)

1. Patients aged 18 to 80 years old
2. Patients diagnosed with aortic arch lesions requiring intervention, including true aortic arch aneurysms, pseudo-aortic arch aneurysms, and ulcers involving the aortic arch.
3. Patients showing a suitable vascular condition, including:
 - Ascending aorta length greater than 50 mm (from the aortic sinusoid junction to the proximal cardiac margin of the innominate artery).
 - Ascending aorta diameter ≥ 24 mm and ≤ 48 mm;
 - Proximal anchoring zone length ≥ 30 mm;
 - Innominate artery diameter ≤ 24 mm and ≥ 6 mm, length ≥ 20 mm;
 - Suitable arterial access for endovascular interventional treatment ;
4. Patients able to understand the purpose of the trial, participate in the trial voluntarily with informed consent form signed by the subject him/herself or his or her legal representative, and willing to complete follow-up visits as required under the protocol.

5. [REDACTED]

[REDACTED]

[REDACTED]

[REDACTED]

[REDACTED]

[REDACTED]

8.1.4.2. Exclusion Criteria (Enrollment will not be allowed if any of the following criteria are met)

1. Patients that have experienced systemic infection during past three months;

2. Neck surgery was performed within three months;
3. Previous endovascular interventional treatment involving the aortic arch was performed;
4. Infectious aortic disease、Takayasu arteritis, Marfan syndrome (or other connective tissue diseases);
5. Patients with severe stenosis, calcification, thrombosis or tortuosity;
6. Heart transplant patients;
7. Patients that have suffered MI or stroke during past three months;
8. Patients with Class IV heart function (NYHA classification);
9. Active peptic ulcers or upper gastrointestinal bleeding occurring within the previous three months;
10. Hematological abnormality, defined as follows: Leukopenia ($WBC < 3 \times 10^9/L$), acute anemia ($Hb < 90 \text{ g/L}$); thrombocytopenia ($PLT \text{ count} < 50 \times 10^9/L$), history of bleeding or coagulopathy;
11. Patients with renal insufficiency, serum creatinine $> 150 \mu\text{mol/L}$, and/or end-stage renal disease requiring renal dialysis;
12. Patients that are pregnant or breastfeeding;
13. Patients with allergies to contrast agents;
14. Patients with a life expectancy of less than 12 months;
15. Patients currently participating in other drug or device research;

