16. Any other disease or abnormality that the investigators believe may hinder endovascular interventional treatment.

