8.1.4.5. Enrollment Timetable

A subject may be enrolled upon obtaining confirmation that a signed informed consent form has been obtained, that the subject meets all entry criteria, and that the subject does not meet any exclusion criteria.

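### Section 7.2 and the exclusion list do not agree: one device contraindication is named in no legible exclusion criterion and another is carried over only for contrast agents

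*Protocol*

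**What the plan says.** Section 7.2 gives four contraindications. The first and the last concern acute systemic infection and vascular anatomy not suited to endovascular repair. Item (2) is worded "Patients with contraindications to antiplatelet and anticoagulant medications". The allergy item, number (3), is worded "Patients with allergies to contrast agents, anesthetic drugs, or materials of the stent and delivery system".

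Section 8.1.4.2 gives 16 exclusion criteria, and the Trial Protocol Summary repeats them. The only allergy criterion is number 13: "Patients with allergies to contrast agents". Two criteria bear on bleeding risk: number 9, "Active peptic ulcers or upper gastrointestinal bleeding occurring within the previous three months", and number 10, a haematological criterion that includes "history of bleeding or coagulopathy". Number 16 is a catch-all: "Any other disease or abnormality that the investigators believe may hinder endovascular interventional treatment".

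Section 8.1.4.5 allows enrolment once consent is confirmed, together with confirmation "that the subject meets all entry criteria, and that the subject does not meet any exclusion criteria". It does not mention Section 7.2.

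**The concern.** A protocol that declares its device contraindicated in certain patients should keep those patients out by rule. Here the rule that controls enrolment looks only at the entry and exclusion criteria, and part of the contraindication list is absent from them. A site that applies 8.1.4.5 exactly as written could enrol, and implant a permanent multi-branch graft in, a patient whom 7.2 describes as contraindicated.

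The protocol itself treats these matters as relevant. Section 14.4.3 lists allergies and arterial thrombosis among potential adverse events. The branch patency endpoint in Section 8.1.6 includes in-stent thrombosis. The notes to the procedure chart in 8.2.1 name anticoagulants and antiplatelet agents among the medications relevant to evaluating the device. Section 6.3 also allows recruitment from emergency departments, where an explicit checklist is most useful.

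There is a consequence for data handling too. Section 9.3 considers removing subjects who were enrolled against the inclusion/exclusion criteria, and Section 15.2 lists the same breach as a protocol violation. A subject who enters through this gap breaches no named criterion, so neither provision would flag the case as an eligibility breach.

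**Working it through.** No arithmetic applies. The check sets each contraindication in 7.2 against the legible criteria in 8.1.4.1 and 8.1.4.2. The summary carries the same criteria.

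| Contraindication in 7.2 | Corresponding criterion | Coverage |
|---|---|---|
| (1) Acute systemic infection | Exclusion 1: "Patients that have experienced systemic infection during past three months" | Covered |
| (2) Contraindication to antiplatelet and anticoagulant drugs | None named; exclusions 9 and 10 cover ulcer, upper GI bleeding, low platelets, bleeding history and coagulopathy | Partial overlap only |
| (3) Allergy, three allergen groups | Exclusion 13, contrast agents | 1 of 3 groups |
| (4) Unsuitable vascular anatomy | Inclusion 3, exclusion 5 | Covered |

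So two of the four items are covered by named criteria, one is covered for one of its three allergen groups, and one is not named at all.

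Next, follow two patients through the rules.

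- *Known allergy to a stent or delivery-system material.* Contraindicated under 7.2(3). None of exclusions 1 to 15 names the condition. Only exclusion 16 could apply, if the investigator believes the allergy may hinder treatment.
- *Hypersensitivity to an antiplatelet drug, with no ulcer, bleeding history, low platelets or coagulopathy.* Contraindicated under 7.2(2) if that item is read as covering either drug class. Exclusions 9 and 10 do not apply. Again only exclusion 16 could.

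Then look for another rule that would close the gap.

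- Section 8.1.4.5 tests consent, entry criteria and exclusion criteria only.
- Section 8.1.8 requires adherence to the screening criteria and has two vascular surgeons per centre record their reasons and the risks for each patient. It requires no check against 7.2.
- The procedure chart in 8.2.1 has a screening row for inclusion/exclusion criteria and none for contraindications.
- Sections 7.3(1) and 21.1(7) require physician and site training. Neither refers to 7.2.

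All 16 exclusion criteria are legible in both places, so blacked-out text does not explain their silence. Inclusion criterion 5 is blacked out in both places and cannot be checked.

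**The case against.** The strongest reply is that the lists are not in logical conflict. Section 7.2 belongs to the same protocol that Section 21.4(2) obliges the principal investigator to follow, no passage directs that a contraindicated patient be implanted, and 8.1.4.5 is permissive. A careful investigator would apply both lists, and a stated contraindication is an obvious use of exclusion 16. The two-surgeon review and the training requirements add further protection, and exclusions 9 and 10 already remove many patients with a bleeding-type reason under item (2).

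Much of this stands. It makes enrolment of such a patient less likely and confines the uncovered part mainly to hypersensitivity. It does not remove the mismatch: every safeguard named works through judgement, none cites 7.2, and centres may apply exclusion 16 differently. Nothing explains why one sentence on allergy was carried over for one allergen group and not for the other two.

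Three stronger readings are tempting and are not supported.

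- A reader might infer that a contraindicated patient can meet every criterion in the protocol. With inclusion criterion 5 blacked out, that cannot be shown.
- A reader might infer that the gap mixes off-indication use into the primary event rate. The indications in 7.1 are lesion types, which these patients would have, and the documents give neither the number of such patients nor any link to extra deaths or major strokes. One event in 90 subjects is 1/90 = 1.1 percentage points, but that is the weight of any subject's event and says nothing specific to this issue.
- A reader might infer that such a subject must remain in every analysis. Section 9.3 also allows removal to be considered on other grounds, including where participation was formally terminated, and the list of violations in 15.2 is open-ended. What follows is only that the case would not be picked up as an inclusion/exclusion violation.

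**Conclusion.** The inconsistency is real and bears on patient safety. Contraindication 7.2(2) is named in no legible exclusion criterion and is only partly overlapped by criteria 9 and 10; 7.2(3) is carried over for contrast agents but not for anaesthetic drugs or device materials. For patients in the uncovered part, exclusion depends on discretion under criterion 16.

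The size cannot be given. The documents do not say how many candidates would fall in the gap, and no prevalence should be assumed. There is no effect on sample size, alpha or power.

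The conclusion rests on the legible criteria. The antiplatelet example also depends on how the word joining the two drug classes in 7.2(2) is read; the device-material example does not. Because the remedy is cheap and the matter concerns who may receive a permanent implant, it should be corrected, although the discretionary safeguards keep it from being more serious than that.

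**What to change.** Reconcile Section 7.2 with the exclusion list in 8.1.4.2, the same list in the Trial Protocol Summary and the enrolment rule in 8.1.4.5, so that contraindications and eligibility agree. Which list is right, and how 7.2(2) is meant to be read, is for the sponsor and investigators to decide; this review does not propose a clinical rule. The screening check should then follow the reconciled text, so that a departure from it is recorded as an eligibility violation under Sections 9.3 and 15.2.

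The cost is a wording amendment with ethics committee approval (Section 15.3) and possibly a few more screen failures.
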